10.5.1.2.4 Additional injection information

- If blanching occurs, the injection should be stopped and the area massaged until it returns to a normal color. Blanching may be a sign of a vascular occlusion. If normal skin coloring does not return, do not continue with the injection. Treat in accordance with the American Society for Dermatologic Surgery guidelines, which include possible hyaluronidase injection. [1]
- Correct to the desired volume effect. Do not overcorrect. The degree and duration of the correction depend on the character of the defect treated, the tissue stress at the implant site, the depth of the implant in the tissue, and the injection technique. Markedly indurated defects may be difficult to correct.
- Follow national, local, or institutional guidelines for use and disposal of medical sharp devices. To help avoid needle or cannula breakage, do not attempt to straighten a bent needle or cannula. Discard it and complete the procedure with a replacement needle from the clinical supply. Do not recap used needles and cannulas. Recapping by hand is a hazardous practice and should be avoided. Discard unshielded needles and cannulas in approved sharps containers.

[figure not shown]

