8 CLINICAL INVESTIGATION PLAN

8.1 Overview of Study Design

This is a prospective, multicenter, randomized, comparative, evaluator-blinded pivotal study designed to evaluate the safety and effectiveness of BBL for the correction of volume loss in the IOH. Study subjects will have a screening period of up to 10 days and participate for a maximum duration of 76 weeks (\pm 14 days).

A total of 150 subjects will be randomized at up to 9 investigational sites in the United States (US). At each study site, the number of subjects randomized should not exceed 26. A minimum of 20% of enrolled subjects will be Fitzpatrick Skin Type IV, V, or VI Subjects from the Fitzpatrick Skin Type IV, V, or VI group will be distributed as follows: at least 16 subjects of Type IV; 7 subjects of Type V; and 7 subjects of Type VI. At least 10% of the subjects enrolled will be male.

Subjects eligible for study enrollment will have symmetrical right and left IOHs with the same MIHAS score of 2 or 3 (moderate or severe), as assessed live by a blinded evaluator. All blinded evaluators will be qualified healthcare practitioners, delegated by the treating investigator and trained by the sponsor. At screening, eligible subjects will be randomized to 4 groups using a 2:2:1:1 ratio as follows: BBL with needle (TN), BBL with cannula (TC), control/delayed-treatment BBL with needle (CDTN), and control/delayed-treatment BBL with cannula (CDTC). The needle or cannula assignment for a subject cannot be interchanged during the study; that is, needle and cannula cannot be used in the same subject.

Subjects randomized to treatment will receive a BBL injection in both IOHs at Day 1. Treated subjects who do not achieve optimal aesthetic correction or at least 1-point improvement on the MIHAS, as assessed by the blinded evaluator 4 weeks post treatment compared to baseline, may have a touch-up injection in one or both IOH(s). If a touch-up is necessary, it will only be administered if there are no medical contraindications or existing AEs of concern, as determined by the treating investigator. The treating investigator will be responsible for reviewing whether the threshold for optimal aesthetic correction or at least 1-point MIHAS improvement is met, as assessed by the blinded evaluator, since the blinded evaluator will not have access to the subject's study records.

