10.5.1.2.1 Assembly of Cannula and Needle

Assembly of Cannula

- To attach the cannula to the syringe, open the cannula packaging to expose the hub.
 Use only the cannula provided with the clinical trial supply.
- 2. Remove the Luer-lock syringe cap from the distal end of the syringe prior to attaching the cannula

3. Holding the Luer-lock fitting of the syringe, twist the cannula onto the syringe. The cannula must be tightened securely to the syringe. Do not over-tighten as this may break the cannula and/or dislodge the syringe

4. Pull off the cannula guard to expose cannula

- Prime the cannula with BBL.
- 6. If excess implant is on the surface of the Luer-lock fitting, it will need to be wiped clean with sterile gauze. Slowly push the syringe plunger until the implant material exudes from the end of the cannula. If leakage is noted at the Luer-lock fitting, it may be necessary to remove the cannula, clean the surfaces of the Luer-lock fitting, and reattach the cannula. In extreme cases, replace both the syringe and the cannula.

Assembly of Needle

Prepare the syringes of BBL injectable implant and the injection needle(s) as described below:

To attach the 27G ½" needle to the syringe, open the needle packaging to expose the needle hub. Use only the 27G ½" needle provided with the clinical trial product. Remove the Luer-syringe cap from the distal end of the syringe prior to attaching the needle

2. Holding the Luer-lock fitting of the syringe, twist the needle onto the syringe. The needle must be tightened securely to the syringe. Do not over-tighten as this may break the needle and/or dislodge the syringe

CCI

4. Prime the needle with BBL injectable implant.

5. If excess implant is on the surface of the Luer-lock fittings, it will need to be wiped clean with sterile gauze. Slowly push the syringe plunger until BBL injectable implant extrudes from the end of the needle. If leakage is noted at the Luer-lock fitting, it may be necessary to remove the needle, clean the surfaces of the Luer-lock fitting, and reattach the needle. In extreme cases, replace both the syringe and the needle.

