10.7 Study Supplies and Packaging of Treatment Supplies

BBL and study accessories (needle, cannula pack) will be provided by the sponsor. The sponsor will package study materials according to applicable regulatory requirements. The sponsor will provide all pertinent labeling information as well as a description of the specific device-packaging conditions.

BBL is to be used exclusively for treatment of subjects enrolled in this study and will be labeled as follows: "CAUTION - Investigational Device. Limited by Federal (or United States) Law to Investigational Use." Device labels will also note the manufacturer name and address, as well as the quantity within the package. The IFU for the investigational product will be provided The clinical trial supply should be stored in a controlled area with limited access and stored separately from any commercial supplies.

The following components are supplied for the injection procedure:

- BBL box containing one sterile 1-mL prefilled glass syringe of BBL with two 27G ½" or 30G ½" needles.
 - o More than one BBL box may be used depending on injection volume.
 - O Use only the 27G ½" needles provided.
 - o If subject is randomized to cannula, these needles should not be used.
- A peel-off subject label, indicating product, to be placed in the source documents.
- A separate bulk supply of 27G 40 millimeter (mm) blunt-tipped cannula, with a 25G introductory needle, will be provided for the cannula-injection procedure.

In the event of a pandemic disease outbreak (e.g., new COVID-19 public health emergency), considerations may be made to supply study sites with sufficient study supplies to avoid interruptions to the supply chain for the investigational product during the outbreak.

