10.10 Treatment Compliance

Treatment is administered by the treating investigator and thus assessment of compliance is unnecessary. Potential deviations from the defined study-treatment administration will be reported as protocol deviations.

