2.1 Clinical Study Design

This is a prospective, multicenter, randomized, comparative, evaluator-blinded pivotal study designed to evaluate the safety and effectiveness of Belotero Balance[®] (+) Lidocaine (BBL) for the correction of volume loss in the Infraorbital Hollow (IOH) area. Study subjects will have a screening period of up to 10 days and participate for a maximum duration of 76 weeks (\pm 14 days).

A total of 150 subjects will be randomized at 9 investigational sites in the United States (US). At each study site, the number of subjects randomized should not exceed 26. A minimum of 20% of enrolled subjects will be Fitzpatrick Skin Type IV, V, or VI. Subjects from the Fitzpatrick Skin Type IV, V, or VI group will be distributed as follows: at least 16 subjects of Type IV; 7 subjects of Type V; and 7 subjects of Type VI. At least 10% of the subjects enrolled will be male.

Subjects eligible for study enrollment will have symmetrical right and left IOHs with the same Merz Infraorbital Hollow Assessment Scale (MIHAS) score of 2 or 3 (moderate or severe), as assessed live by a blinded evaluator. All blinded evaluators will be qualified healthcare practitioners, delegated by the treating investigator and trained by the sponsor. At screening, eligible subjects will be randomized to 4 groups using a 2:2:1:1 ratio as follows: BBL with needle (TN), BBL with cannula (TC), control/delayed-treatment BBL with needle (CDTN), and control/delayed-treatment BBL with cannula (CDTC). The needle or cannula assignment for a subject cannot be interchanged during the study; that is, needle and cannula cannot be used in the same subject.

Subjects randomized to treatment (TN or TC) will receive a BBL injection in both IOHs at Day 1. Treated subjects who do not achieve optimal aesthetic correction or at least 1-point improvement on the MIHAS, as assessed by the blinded evaluator 4 weeks post treatment compared to baseline, may have a touch-up injection in one or both IOH(s). If a touch-up is necessary, it will only be administered if there are no medical contraindications or existing adverse events (AEs) of concern,

as determined by the treating investigator. The treating investigator will be responsible for reviewing whether the threshold for optimal aesthetic correction or at least 1-point MIHAS improvement is met, as assessed by the blinded evaluator, since the blinded evaluator will not have access to the subject's study records.

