The randomized population will consist all subjects randomized.

Safety Population (SP)

The SP will consist of all subjects treated.

Intent-to-Treat (ITT) Population

The ITT population will include all randomized subjects of the control group (CTL) and all randomized and treated subjects of the treatment group (TRT).

Per Protocol (PP) Population

The PP population is a subset of subjects in the ITT population without major protocol deviations (PDs). Final determination of what constitutes a major protocol deviation leading to exclusion from PP population will be made in a data review meeting (DRM) prior to database close.

Analyses based on ITT and PP populations and effectiveness analyses based on SP will include subjects as randomized. All other analyses on the SP will include subjects as treated.

5 Endpoints for Analysis

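### The bent-cannula instruction in Protocol 10.5.1.2.4 tells the injector to finish with a needle, against the rule that one subject never receives both devices

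*Protocol*

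**What the plan says.** The last bullet of Protocol Section 10.5.1.2.4 deals with handling and disposal of sharps. It covers a bent device of either kind, and its replacement sentence reads "Discard it and complete the procedure with a replacement needle from the clinical supply". It does not mention a replacement cannula.

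Other parts of the plan treat the injection device as fixed for each subject:

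- Protocol Section 8.1, on the four randomized groups: "that is, needle and cannula cannot be used in the same subject".
- SAP Section 2.1: "The needle or cannula assignment for a subject cannot be interchanged during the study".
- Protocol Section 10.7, on the needles packed in the product box: "If subject is randomized to cannula, these needles should not be used". The same section lists "A separate bulk supply of 27G 40 millimeter (mm) blunt-tipped cannula", so spare cannulas are provided.
- Protocol Section 10.5.1.2.1, on leakage at the cannula fitting: "In extreme cases, replace both the syringe and the cannula". That remedy keeps the subject on a cannula.

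On consequences, Protocol Section 10.10 states "Potential deviations from the defined study-treatment administration will be reported as protocol deviations", and SAP Section 4 states "Analyses based on ITT and PP populations and effectiveness analyses based on SP will include subjects as randomized". The other analyses on the safety population are as treated.

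**The concern.** Needle versus cannula is a randomized factor, allocated 2:2:1:1 across the needle (TN) and cannula (TC) treatment groups and the two delayed-treatment groups. It has its own sequential tests against control: Hypothesis 3 for needle and Hypothesis 4 for cannula. Safety is also summarized by technique, in the pooled needle (NED) and cannula (CAN) groups.

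An injector who bends a cannula and obeys Section 10.5.1.2.4 literally would give the rest of the volume by needle. That breaks the assignment rule and creates a protocol deviation. It puts some needle-delivered product into the cannula arm of Hypothesis 4. It also leaves open whether the subject belongs to NED or CAN in the as-treated safety tables, because the definitions of those groups give no rule for a subject injected with both devices.

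**Working it through.** **Reading the texts together**

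1. *Scope.* The bullet names both devices when it speaks of breakage, bending, recapping and disposal. Only the replacement sentence drops the cannula. The thing to be discarded is whichever device bent, so for a bent cannula the literal instruction is to finish with a needle.
2. *Is there an exception?* None appears in the available text of the protocol or SAP.
3. *Could the introductory needle be meant?* No. Under Section 10.5.1.2.3.1 that needle makes the skin puncture and is withdrawn before the cannula goes in. It cannot complete an injection.
4. *Is the sentence damaged?* It is complete and grammatical, with no redaction mark inside it.

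The contradiction is therefore with explicit rules in Protocol Sections 8.1 and 10.7 and SAP Section 2.1.

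**How much could it matter?** The plan states no figure on this point, so there is none to reproduce. What follows is a scale check.

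*Inputs from Protocol Section 13.2:* 50 TC subjects, 25 control/delayed-treatment cannula subjects (CDTC), 50 controls in all, response 70% versus 30%, drop-out up to 20%. *Inputs from the treatment schedule:* TC subjects have at most 3 sessions (initial, touch-up, retreatment) and CDTC subjects at most 2 (initial, touch-up).

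*Assumptions, not in the documents:* a bend in 1% to 3% of sessions, a touch-up in every subject, a needle switch after every bend, and a response of 60% or 80% in a switched subject.

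- Cannula sessions in the whole study: 50 × 3 + 25 × 2 = 200 at most.
- Sessions before the TC Week 8 endpoint: 50 × 2 = 100 at most.
- TC subjects affected before that endpoint: 50 × [1 − (1 − p)²].
  - p = 0.01: 50 × (1 − 0.9801) = 1.0.
  - p = 0.03: 50 × (1 − 0.9409) = 3.0.
- TC response rate if 3 of 50 (6%) switch:
  - needle response 60%: 0.94 × 0.70 + 0.06 × 0.60 = 0.694.
  - needle response 80%: 0.94 × 0.70 + 0.06 × 0.80 = 0.706.

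Power for Hypothesis 4 taken alone was found by enumerating every pair of response counts and applying the plan's rule that the lower Newcombe limit exceeds zero. The calculation used 40 TC and 40 control subjects (50 × 0.80 in each):

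| TC response | Control response | Power |
|---|---|---|
| 0.700 (no switches) | 0.30 | 96.4% |
| 0.694 | 0.30 | 95.9% |
| 0.706 | 0.30 | 96.8% |

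The change is about half a percentage point in either direction.

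**The case against.** The strongest reply is that no site would be misled. The assignment rule is explicit, Section 10.7 speaks directly to cannula subjects, spare cannulas are in stock, and the faulty sentence sits in a general sharps bullet. Read with the rest, it means like-for-like replacement. That is probably the intent, and it is why the point is minor. It does not make the sentence correct: this is an operative instruction in the injection section, and it gives a cannula-arm injector the opposite direction from Section 8.1.

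Several narrower replies stand in part:

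- The bend and needle-response rates have no source in the documents. The counts of 1 to 3 subjects are conditional on the assumed rates and do not bound what could happen.
- Hypothesis 4 is tested only after Hypotheses 1 to 3 are rejected, so its power taken alone is not its power within the sequence. The planned analysis also imputes missing Week 8 scores. With 50 versus 50 complete, the baseline power is 98.8%. Neither fact makes the effect larger in any way that matters.
- The leakage rule in Section 10.5.1.2.1 concerns a different fault. It shows intent and is not itself contradicted.
- A switch would not be invisible. It is a protocol deviation, and the SAP summarizes injection technique for each treatment and each side.
- The version history shows that all control subjects had completed their Week 8 visit by version 5.0, so most initial cannula injections had very likely been given. A correction now would reach mainly later sessions, such as TC retreatments.
- The separate instructions for use were not available here and may say more about bent cannulas.

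**Conclusion.** The concern holds. For a bent cannula, Section 10.5.1.2.4 is wrong as written and conflicts with explicit rules elsewhere in the protocol and in the SAP. It is a minor wording error.

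Its frequency cannot be determined from the documents. Under the assumed rates, the effect on the cannula-versus-control test is negligible. The primary tests pool needle and cannula subjects, so neither they nor the sample size depends on this point. The only other analysis effect is a slight blurring of the technique-specific safety summaries if a switch occurs.

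**What to change.** Reword the sentence so that the injector discards the bent device and completes the procedure with *a replacement needle or cannula of the type to which the subject was randomized*, taken from the clinical supply. Send sites a short notice covering any injections still to be given.

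The cost is one phrase in the protocol and the notice. Replacement cannulas are already supplied in bulk. No new data, additional subjects or SAP change is needed.

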10.5.1.2.5 Post-Treatment Care/Pain Management

- To manage post-injection pain, ice may be applied, as needed.
- Acetaminophen may be taken if instructed by the treating investigator. Any medication or therapy used by the subject must be recorded in the eCRF.
- The following information should be shared with subjects:
 - O Within the first 24 hours, subjects should avoid lower eyelid makeup, strenuous exercise, extensive sun, or heat exposure, aspirin or non-steroidal anti-inflammatory drugs, and alcoholic beverages. Exposure to any of the above may cause temporary redness, swelling, and/or itching at the injection site.
 - Any and all medications or non-drug therapies used throughout study participation should be reported by the subject to site personnel for recording in the eCRF.

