9.2.3 Subject Restrictions during the Study

By providing informed consent, subjects are also prohibited from the following actions and treatments after injection:

- Touching/pressing the treatment area for 12 hours after treatment.
- Applying makeup to the treatment area for 12 hours after treatment.
- Exercising strenuously for 24 hours after treatment.
- Consuming alcoholic beverages for 24 hours after treatment.
- Exposing the treated area to extensive sun or heat exposure for 24 hours after treatment.

- Receiving any other procedures (i.e., dermal fillers, fat injections, facial ablative or fractional laser, microderm abrasion, superficial or deep chemical peels, platelet-rich plasma, non-invasive skin-tightening [e.g., Ultherapy, Thermage], mesotherapy, or any surgical procedures) on ANY part of the face during study participation.
- Receiving neurotoxin treatment in ANY part of the face.
- Initiation of any new topical over-the-counter or prescription facial skin product or oral medication that affects the facial appearance.
- Using prescription topical steroids on the face.
- Receiving anti-coagulation, anti-platelet, or thrombolytic medications (e.g., warfarin), anti-inflammatory drugs (e.g., oral/injectable corticosteroids or NSAIDs [e.g., aspirin, ibuprofen]), or other substances known to increase coagulation time (e.g., vitamins or herbal supplements, [e.g., Vitamin E, fish oil, garlic, gingko, St. John's Wort]) from 10 days before injection to 3 days after injection.
- Receiving immunosuppressive medications or systemic steroids (except intranasal/inhaled or intra-articular steroids).
- Gaining or losing ≥ 2 BMI units.
- Prolonged exposure of the face to UV radiation (sun, tanning bed).
- Oral surgery (e.g., orthodontia, extraction, implants).

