10.6 Previous and Concomitant Non-drug Therapies

Previous therapies received prior to enrollment and concomitant therapies should be documented in the eCRF.

Restrictions regarding prior or concomitant non-drug therapies are discussed in detail in Sections 9.2.2 (Exclusion Criteria) and 9.2.3 (Restrictions during the Study).

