In the event of intravascular injection or embolic event, the treating physician will provide prompt medical attention and follow the proper protocol in accordance with the American Society for Dermatologic Surgery guidelines.[1] If the injection is in progress, best practices should be used to stop the injection. The treating physician should consider the following: an immediate referral to the site-identified ophthalmology practice, injection of hyaluronidase (if applicable) in the anatomic area of treatment and/or retrobulbar, and consideration of active reduction of intraocular pressure. The investigator should treat in accordance with the American Society for Dermatologic Surgery guidelines.[1]

11.2.2.2.2 72-hour Post Treatment Phone Call

All subjects will receive a post-treatment phone call 72 hours (+ 1 day) after the initial treatment, after the touch-up treatment, if applicable, and/or after optional retreatment.

During this phone call, study personnel will discuss and record any changes in concomitant medications/procedures and confirm that the subject remains compliant with any applicable study restrictions. Study personnel will also discuss the completion of the subject eDiary and remind the subject how to utilize the eDiary for daily entries. If there are any safety concerns that would necessitate an unscheduled visit to the site, this visit should be scheduled during the phone call.

In addition, each subject will be asked if he/she experiences any new or unusual symptoms related to a potential vascular occlusion (e.g., signs of a stroke, changes in vision, tissue necrosis) as noted in the Study Information Guide for Subjects. If any other such symptoms related to a potential vascular occlusion are reported by the subject, he/she should be assessed, and referred for immediate medical treatment as deemed necessary per best medical practices. If any change in vision is reported during the 72-hour follow-up phone call, the subject may be referred immediately to the site-identified ophthalmology practice or a local emergency room (if the ophthalmology practice cannot be reached or is not available) for further evaluation.

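### Post-treatment advice limits aspirin and NSAIDs for 24 hours only, while Section 9.2.3 prohibits them until 3 days after injection

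*Protocol*

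**What the plan says.** Two current sections of the protocol set a period for aspirin and NSAIDs around an injection.

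- **Section 10.5.1.2.5 (Post-Treatment Care/Pain Management)** lists information for sites to pass on to subjects. It includes: "Within the first 24 hours, subjects should avoid lower eyelid makeup, strenuous exercise, extensive sun, or heat exposure, aspirin or non-steroidal anti-inflammatory drugs", followed by alcohol. The reason given is possible temporary redness, swelling or itching at the injection site. For pain, the section allows ice as needed, and "Acetaminophen may be taken if instructed by the treating investigator".
- **Section 9.2.3 (Subject Restrictions during the Study)** opens with "By providing informed consent, subjects are also prohibited from the following actions and treatments after injection". One item covers anticoagulant, antiplatelet and thrombolytic drugs, "anti-inflammatory drugs (e.g., oral/injectable corticosteroids or NSAIDs [e.g., aspirin, ibuprofen", and so on, "or other substances known to increase coagulation time". The period for the whole item is "from 10 days before injection to 3 days after injection".

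Section 10.5.1.2.5 does not cite Section 9.2.3. Section 10.6, shortly afterwards, does cite it, but only for non-drug treatment: "Restrictions regarding prior or concomitant non-drug therapies are discussed in detail in Sections 9.2.2 (Exclusion Criteria) and 9.2.3 (Restrictions during the Study".

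On follow-up, Section 11.2.2.2.2 states: "All subjects will receive a post-treatment phone call 72 hours (+ 1 day) after the initial treatment", with the same call after a touch-up or retreatment. Staff use the call to record medication changes and to confirm that the subject is keeping to the study restrictions.

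**The concern.** Section 10.5.1.2.5 is the text that site staff would use when sending a subject home. An end time of 24 hours invites the inference that the limit stops there. A subject relying on that advice alone could take ibuprofen or aspirin on the second or third day and breach Section 9.2.3 without knowing it.

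The stated reasons differ as well as the periods. The after-care text presents the limit as a matter of short-lived local irritation. Section 9.2.3 puts NSAIDs in the same item as anticoagulants and agents that prolong coagulation. A subject who hears only the first message gets a shorter period and a milder reason.

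What is at stake is the accuracy of safety advice and the avoidance of needless protocol deviations. No endpoint, sample size or test is involved.

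**Working it through.** The check is a comparison of text, with one subtraction.

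**1. The after-care list against Section 9.2.3, item by item**

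| Item | Section 9.2.3 | Section 10.5.1.2.5 | Advice compared with restriction |
|---|---|---|---|
| Strenuous exercise | 24 h after | 24 h after | same |
| Alcohol | 24 h after | 24 h after | same |
| Extensive sun or heat | 24 h after | 24 h after | same |
| Makeup | 12 h after | 24 h after | longer (stricter) |
| Aspirin/NSAIDs | 10 days before to 3 days after | 24 h after | **shorter** |

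Section 9.2.3 also has a separate item, without a time limit, against prolonged UV exposure of the face. The table compares the matching 24-hour items.

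Three of the five items agree exactly, so the list reads like a summary of Section 9.2.3. Makeup differs in the safe direction: following the advice cannot breach the restriction. Aspirin/NSAIDs is the only item whose stated period is shorter than the one Section 9.2.3 sets for it.

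**2. Size of the gap**

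- Prohibited period after injection, reading 3 days as 72 hours: 3 × 24 h = 72 h.
- Period named in the advice: 24 h.
- Prohibited but not named: 72 h − 24 h = 48 h, running from 24 h to 72 h after injection.

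**3. Whether a scheduled contact falls inside the gap**

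- Phone call window: 72 h to 72 h + 24 h = 96 h after injection.
- The earliest call therefore falls at the end of the gap. It can detect NSAID use between 24 and 72 hours but cannot prevent it.

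**4. Whether a cross-reference closes the gap**

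Section 10.5.1.2.5 has none. The pointer in Section 10.6 is worded for non-drug therapies and does not reach aspirin or NSAIDs.

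**5. What cannot be calculated**

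The documents do not show how many subjects would take an NSAID in the gap, how many are told the 3-day rule elsewhere, or how many injections remain under version 5.0. No count of affected subjects is given.

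**The case against.** The strongest reply is that the sections do not contradict each other. Section 10.5.1.2.5 permits nothing after 24 hours, and a subject who follows Section 9.2.3 satisfies both. The after-care list has its own stated purpose and does not restate Section 9.2.3, most of which it omits. This is correct, and it makes the fault one of incomplete and potentially misleading advice, not of conflicting orders. It does not remove the fault: a stated end time shorter than the actual restriction says more than silence would.

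A second reply is that subjects probably learn the 3-day rule elsewhere. The restrictions are tied to informed consent. The 3-day limit shares a sentence with the 10-day pre-injection limit, which subjects need to know before treatment. Section 11.2.2.2.2 also mentions a Study Information Guide for Subjects. Neither the consent form nor the guide is available here, and either may give the full period. This stands as a limit on how often a breach would occur. Even so, staff following Section 10.5.1.2.5 would be giving advice shorter than the written restriction.

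Third, ice and investigator-directed acetaminophen are the only pain measures named, so NSAID use for injection pain is less likely. That also stands, but it does not cover aspirin or ibuprofen taken for another reason.

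Finally, few injections may remain. The version 5.0 amendment summary says all control/delayed-treatment subjects had already completed Visit C1-a, the delayed-treatment baseline. Touch-ups and retreatments may still be to come, in a number the documents do not give.

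**Conclusion.** The concern holds as a minor point. The aspirin/NSAID period in the advice to subjects is shorter than the restriction in Section 9.2.3 by 48 of 72 post-injection hours, and nothing in Section 10.5.1.2.5 directs the reader to the longer period. The 48-hour figure rests on reading 3 days as 72 hours.

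Confidence is high that the two texts differ. There is no basis for saying how often the difference would lead to a breach, because that depends on subject material that is not available and on the number of injections remaining. The consequence is confined to safety advice and avoidable deviations; power and the primary analysis do not change.

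**What to change.** In Section 10.5.1.2.5, take aspirin and NSAIDs out of the 24-hour list and add one sentence: *Aspirin and NSAIDs are prohibited from 10 days before to 3 days after each injection (see Section 9.2.3).* Check the consent form and the subject guide, and make the same correction wherever the 24-hour wording is repeated.

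The drafting cost is one sentence per document. Because it is a protocol modification, it needs IEC/IRB approval under Section 14.6; if the consent form changes too, the amended-form requirements in Section 5.2 apply. Section 9.2.3, the visit schedule, the sample size and the analysis stay as they are.
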